7.5.4 Visit and instrument schedule

The following schedule of visits will be followed:

Tools	6 weeks visit	Extra visit
EPDS	In chosen language	In same language
MIB	In chosen language	In same language
FSS-5R	In chosen language	In same language
WHOQOL-BREF	In chosen language	In same language

7.5.5 Data collection

Data will be collected electronically using REDCap. Surveys will not be anonymous as it will be necessary to link the two visits for each participant.

The preferred language selected by the participant for the main study will be the preferred language for this sub-study. All participants will complete the instrument in the same preferred language on the date of the 6 weeks' visit, as well as at an extra study visit.

7.5.6 Ethical considerations

Verbal consent will be sought from each individual participant for inclusion in the sub-study. All participants will have their transportation cost for the extra clinic visit reimbursed.

7.5.7 Sample size

The sample size required was determined to be 118 per language based on a median of the sample sizes that have worked well for previous studies among patients (40). For the EPDS, the sample size for some published translation and validation studies have been 87(41), 100(42), 118(43), 123(44), and 451(45). For the MIB, sample sizes that have worked well include 63(46) and 554(47). For the FSS, the sample size for published translation and validation studies have included 23(48), 83(49), 113(50), 123(51), and 427(52). For the WHOQOL-BREF, sample sizes that have worked well include 228(53) and 538(44).

7.5.8 Data analysis

All analyses will be completed using R and RStudio. Test-retest reliability will be assessed using Pearson correlation.

8 Implementation research

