Study design	A multicenter parallel, open label, superiority randomized controlled trial, with an alongside implementation study.
Aims	To determine the clinical effectiveness, tolerability, and safety of intravenous ferric carboxymaltose (intervention) versus oral ferrous sulphate (control) for treating iron deficiency anemia in postpartum women.
	To evaluate the implementation outcomes (acceptability and feasibility) of using intravenous ferric carboxymaltose in treating postpartum anemia in Nigeria.
Objective(s)	 To determine the clinical effectiveness of intravenous ferric carboxymaltose versus oral ferrous sulphate in postpartum women with moderate to severe iron deficiency anemia. To determine the incidence of adverse drug events including the incidence of hypophosphatemia in the mother and adherence with the use of intravenous ferric carboxymaltose and oral ferrous sulphate for treatment of postpartum anemia. We will measure Vitamin D, alkaline phosphatase, total procollagen type 1 N-terminal propeptide (P1NP), fibroblast growth factor 23 (FGF23), calcium (Ca), phosphate (PO₄), which are biomarkers of phosphorus homeostasis and bone turnover. To determine the acceptability of Intravenous Ferric carboxymaltose to women and health care professionals

	• To determine the feasibility and organizational readiness for implementing the use of intravenous ferric carboxymaltose in treating postpartum anemia in Nigeria.
Number of participants	1,400 women
Participant selection criteria	 Women aged 15 to 49 years. Between six and 48 hours after birth. Baseline (enrolment) moderate or severe anemia (Hb < 10g/dl). Able and willing to give written informed consent
Intervention product, dose, and route of administration	Ferric carboxymaltose, single dose of 20mg/kg (not exceeding 1000mg), Intravenous route
(Control) product, dose, and route of administration	Ferrous sulphate, 200mg (65mg elemental iron) two times daily. Oral route.
Duration of each woman's participation	6 months
Follow-up	2 weeks (±3 days), 6 (±1) weeks, 12 (±2) weeks and 6(±1) months postpartum.
Study duration	36-months

[figure not shown]

TABLE OF CONTENTS

ATTESTA	ATIONS	4
PROTOC	COL SYNOPSIS	5
TABLE O	OF CONTENTS	7
LIST OF 1	TABLES	11
LIST OF I	FIGURES	11
LIST OF A	ABBREVIATIONS	12
GLOSSAI	RY OF TERMS	13
INTRODI	UCTION	14
1.1	Background	14
2 STUDY	Y OBJECTIVES	17
2.1	Aims	17
2.2	Objectives	17
з оитсс	OMES	18
3.1	Clinical outcomes	18
3.2	Implementation outcomes	19
4 STUDY	Y DESIGN	20

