4.6 Study intervention

4.6.1 Administration of study drugs

Administration of ferric carboxymaltose (FCM): Eligible women randomized to the intervention arm (FCM) will be observed at the dedicated ward or daycare room for treatment initiation and will be given intravenous ferric carboxymaltose (FCM) in a single dose of 20mg/kg up to a maximum of 1000mg. This dose will be administered as an infusion diluted in 200 ml 0.9% sodium chloride and infused over a minimum of 15 - 20 minutes (Table 2). Thereafter, they will be observed closely for a minimum of 30 minutes after infusion. [Refer to IVON-PP Trial - Protocol for the administration of Intravenous Ferric

Carboxymaltose and the Emergency Treatment of Hypersensitivity Reaction Type 1 (Anaphylaxis); Protocol no 2].

Administration of Ferrous Sulphate (FS): The women randomized to the control arm (FS) will be given for take home, one **200mg tablet of study drug, ferrous sulphate** which contains 65mg of elemental iron, to be taken two times daily and 1 hour before meals or 2 hours after meals with a full glass of water till 6 weeks postpartum (Table 2). The study drug for the control arm (FS) will be prepared in sachets, dispensed, and packaged in 2-week, 4-week and 6-week doses for the appropriate visit schedule. The women will be sent daily reminders by text messages and asked to bring in their empty sachets for sighting and for a pill count and evaluation of compliance at each study visit.

Table 2: Oral and intravenous Iron dosing for intervention and control arms

Study arm	Study medications	Dose	Comments
Intervention	Drug: intravenous ferric carboxymaltose	Single dose of 20mg/kg (to a maximum of 1000mg)	A dose of 20mg/kg body weight (but not exceeding a max of 1,000mg) of ferric carboxymaltose will be given in 200mls of normal saline as a single dose infusion administered over 15 – 20 minutes
Control	Drug: oral ferrous sulphate	One 200mg tablet (65 mg elemental iron) 2 times daily	Treat with 2 times daily regimen till six weeks postpartum. ^{a, b}

a. All patients will also receive 5mg folic acid daily and 400mg Vitamin C daily.

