7.5.2 Study population

A sample of women with an upcoming six-week visit will be selected for the sub-study. Consent into the validation sub-study will take place at enrolment into IVON-PP trial or at the two weeks' visit. All women enrolled in the study in November 2023 and onwards will be considered for inclusion in the validation sub-study.

To be eligible for the sub-study, participants must be:

- 1) Eligible for and enrolled in the IVON-PP trial.
- 2) Willing to attend one extra visit around the time of the six weeks' visit.

Participants' health status or randomization arm will not, otherwise, be a basis for inclusion or exclusion. Participants' informed verbal consent will be sought.

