7.5.3 Study design

Participants will be invited to attend an extra postpartum visit, one to four weeks before or after their scheduled 6 weeks' postpartum visit, at the participants' convenience. The study team will follow the regular study visit schedule (2 weeks and 6 weeks post-partum) to the extent possible, and schedule additional visits as necessary.

All consecutive study participants will be invited to participate until the minimum sample size for the chosen language is reached.

To the extent possible, the extra visit will be conducted in the same manner as the scheduled six weeks' visit. That is, if the scheduled six weeks' visit occurs as a physical in- hospital or at the participant's home, then the extra visit will take place at the same site as the study schedule visit. The same will apply for visits completed virtually.

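### The validation sub-study judges test-retest reliability by Pearson correlation alone, which cannot show a systematic shift between visits that may be weeks apart during recovery from anemia

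*Protocol*

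**What the plan says.** Section 7.5.1 of the protocol gives the validation sub-study one objective: the test-retest reliability, in Nigerian languages, of the depression, fatigue, bonding and quality-of-life scales. Apart from naming the software, section 7.5.8 consists of one sentence on analysis: "Test-retest reliability will be assessed using Pearson correlation".

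Section 7.5.3 places the extra visit "one to four weeks before or after their scheduled 6 weeks' postpartum visit, at the participants' convenience". It then adds: "The study team will follow the regular study visit schedule (2 weeks and 6 weeks post-partum) to the extent possible", with further visits scheduled as needed. The follow-up row of the synopsis gives the visit windows as "2 weeks (±3 days), 6 (±1) weeks, 12 (±2) weeks and 6(±1) months postpartum".

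Section 7.5.2 does not select stable women or a single arm: "Participants' health status or randomization arm will not, otherwise, be a basis for inclusion or exclusion". On treatment, section 4.6.1 says that women in the intervention arm "will be given intravenous ferric carboxymaltose (FCM) in a single dose of 20mg/kg up to a maximum of 1000mg". For the control arm, Table 2 says "Treat with 2 times daily regimen till six weeks postpartum".

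Section 7.5.7 sets 118 women per language, from the sizes of earlier validation studies. Section 7.5 gives no target coefficient, precision or threshold for acceptable reliability.

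**The concern.** Test-retest reliability asks whether the same woman gets nearly the same score twice when nothing has changed. Pearson correlation answers a narrower question: whether the two sets of scores lie on a straight line. If every woman scored several points lower at the second visit, the coefficient could still be close to 1.

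The design gives room for such movement. Every participant enters with moderate or severe anemia and is treated for it. Section 1.1 links postnatal anemia to fatigue, depression and weaker bonding, and section 3.1.2 makes depression, fatigue, bonding and quality of life secondary outcomes of the trial. Over a gap of weeks, scores may move for real. The part of the movement common to all women is invisible to Pearson. The part that differs between women lowers the coefficient and looks like a poor instrument.

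At stake is the meaning of the sub-study's only result. A high coefficient would not exclude a systematic shift, and a low one would not separate a noisy scale from women who changed.

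**Working it through.** **The plan's own figure.** The five depression-scale study sizes in section 7.5.7 are 87, 100, 118, 123 and 451. Their median is 118, so the stated figure is reproduced. The median of all 14 sizes listed there for the four scales is (118 + 123)/2 = 120.5, which is close. No target correlation or precision is given, so there is no power calculation to check.

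**Length of the gap.** Two weeks ±3 days is day 11 to day 17. Six ±1 weeks is day 35 to day 49.

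- Shortest in-window gap between these visits: 35 − 17 = 18 days.
- Nominal gap: 42 − 14 = 28 days.
- Longest in-window gap: 49 − 11 = 38 days, or 38/7 = 5.4 weeks.

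No in-window pair from the regular 2-week and 6-week visits is therefore within 14 days.

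**Effect of a common shift.** Assume equal variances at the two visits, correlation r, and a mean shift of d standard deviations. Pearson stays at r for any d. With two visits, the between-visit variance is d²/2 in SD² units, so

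absolute-agreement ICC = r / (1 + d²/2).

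The consistency form leaves out the between-visit term and equals r under equal variances. All values of r and d below are assumptions, because the protocol gives none.

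| r | d | Pearson | Absolute-agreement ICC |
|---|---|---|---|
| 0.85 | 0.25 | 0.85 | 0.85/1.03125 = 0.82 |
| 0.85 | 0.5 | 0.85 | 0.85/1.125 = 0.76 |
| 0.85 | 0.8 | 0.85 | 0.85/1.32 = 0.64 |
| 0.80 | 0.5 | 0.80 | 0.80/1.125 = 0.71 |
| 0.90 | 0.5 | 0.90 | 0.90/1.125 = 0.80 |

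A simulation at n = 118 (2,000 runs) with r = 0.80 and d = 0.5 gave a mean Pearson of 0.80 and a mean absolute-agreement ICC of 0.71, as the formula predicts.

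**Effect of change that differs between women.** Let the individual true change have SD s, in units of the first-visit SD, and be independent of the first score. The second-visit variance becomes 1 + s², and

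Pearson = reliability / √(1 + s²).

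With reliability 0.80 (assumed):

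- s = 0.3: 0.80/√1.09 = 0.77
- s = 0.5: 0.80/√1.25 = 0.72
- s = 0.7: 0.80/√1.49 = 0.66

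For scale, the 95% CI around r = 0.80 at n = 118 is 0.72 to 0.86. A change SD of about 0.5 therefore moves the expected estimate to the lower limit of that interval.

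**What an ICC does not repair.** With reliability 0.80, s = 0.5 and no mean shift, the simulated absolute-agreement ICC was 0.71, almost the same as Pearson (also 0.71 in the simulation). With a shift of 0.5 SD added, it fell to 0.64. An agreement coefficient makes a shift visible, but it cannot say whether the shift is instrument error or recovery.

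**The case against.** The strongest reply is that, if women are recovering, a common shift is true change. Absolute agreement then charges that change to the scale, whereas Pearson leaves it out. This stands. It is the reason to report both forms of the ICC with the mean difference, and not to put absolute agreement alone in Pearson's place.

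A reader might infer that all women are retested while on iron treatment. The documents do not support that. The intervention arm has one infusion at enrolment, and scheduled oral iron ends at six weeks. The statement holds only for the control arm when the extra visit comes before week 6. What remains is that women in either arm may still be recovering.

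A reader might also infer that most pairs will be four weeks apart. Section 7.5.3 can be read that way. However, section 7.5.2 speaks of one extra visit near the six-week visit, the schedule in 7.5.4 lists only the 6-week and extra visits, and Table 3 places none of the four scales at two weeks. The share of long gaps is unknown.

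Finally, the size is hypothetical and the reach is small. A shift of 0.25 SD costs only 0.03 (0.85 against 0.82). No threshold is set, so nothing in the text would declare a scale reliable or unreliable. The main trial uses the scales whatever the coefficient, and it compares the arms at the same visits, so a time shift common to both arms largely cancels. These points limit the weight of the concern. They do not make Pearson a measure of agreement.

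**Conclusion.** The concern holds, within limits. Section 7.5.8 commits the sub-study's only objective to a statistic that cannot detect a systematic shift between visits. This is a stated choice of method, not a detail left open, and the blindness is algebraic whatever shift is assumed. The size in practice is unknown: at r = 0.85 with equal variances, the gap between Pearson and absolute agreement runs from 0.03 at a shift of 0.25 SD to 0.21 at 0.8 SD (0.85 − 0.64). These shifts are assumptions, as is the amount of individual change.

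Two stronger conclusions are tempting but do not follow. One is that the plan will pass bad scales or fail good ones; the protocol contains no such decision rule. The other is that restricting the analysis to pairs one to two weeks apart would settle the matter. If the regular visits are used, in-window pairs are at least 18 days apart, so that subset could be nearly empty. The impact is confined to the validation sub-study, and the primary outcome, hemoglobin at six weeks, is untouched.

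**What to change.** In section 7.5.8, replace Pearson correlation with the following, per scale and per language:

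- the two-way intraclass correlation with 95% CI, in both the absolute-agreement and the consistency form;
- the mean difference between visits and the limits of agreement.

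Report these by length of gap, and state that absolute agreement over the longer gaps mixes instrument error with true change. A clear difference between the two forms, read with the mean difference, shows the shift that Pearson hides.

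This part needs only a change of wording and a few lines of code on the paired data already planned. Results split by gap rest on fewer than 118 women per language, so their intervals will be wider.

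If a short-gap result is wanted, an analysis change is not enough. The sentence in 7.5.3 that favours the 2-week and 6-week schedule would also have to be amended while sub-study visits are still being booked, which means rescheduling visits and amending the protocol.

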8.1 Theoretical framework for implementation research

New innovations (and existing innovations introduced into new contexts) commonly fail due to challenges with adoption, adaptation, and implementation (30, 31). This is particularly common in LMICs. Determinants of successful implementation of an innovation range across systemic, economic, policy and individual factors. These determinants could either facilitate or impede the observed effectiveness and sustainability of efficacious interventions. Thus, hybrid trials seek to evaluate the effectiveness of interventions as well as understand strategies and contexts suitable for optimal and sustained implementation (32). Implementation science has evolved theories, models, and frameworks to guide the understanding of the implementation climate, and to improve implementation of outcomes (33). Implementation climate has been defined as "targeted employees' shared summary perceptions of the extent to which their use of a specific innovation is rewarded, supported, and expected within an organization" (34). Whereas outcomes of implementation are considered as the direct effects of deliberate and purposive actions to implement innovations (35). These outcomes include acceptability and feasibility.

This study will be guided by the Consolidated Framework for Implementation Research (CFIR) (36) and the Reach-Effectiveness-Adoption-Implementation-Maintenance (RE-AIM) framework (37) to understand how contextual determinants and implementation climate impact on implementation outcomes. The CFIR will explore five major domains, each of which may affect implementation of ferric carboxymaltose in Nigeria. There are the intervention characteristics (e.g., stakeholders' perceptions about the relative advantage of implementing the intervention, intervention complexity), inner setting (e.g., implementation climate, leadership engagement), outer setting (e.g., external policies and incentives), characteristics of individuals involved in implementation (e.g., knowledge and beliefs about the intervention), and the implementation process (Figure 3).

Figure 3: Implementation evaluation guided by the Consolidated Framework for Implementation Research (CFIR)

Intervention Characteristics	❖ Feasibility		
	❖Intervention Complexity		
	❖Assess Cost		
Inner Settings	❖ Health System's Organizational		
	Structure		Accontability
	❖ Health System's Organizational		Acceptability
	Culture	Implementation	
	❖ Readiness to Implement	Outcomes	
Outer Settings	❖External Policy Environment		Feasibility
	(Existing Policies and Processes)		
Individuals Involved	❖Stakeholders' interests		
	Acceptability		
Implementation Process	❖Implementation Strategies		

8.2 Study population

We plan to work with multiple stakeholders for the implementation research. They will include:

- Postpartum women with and without anemia (between two to six weeks postpartum)
- Postpartum women with past or current anemia treatment (between two to six weeks postpartum)
- Male partners of postpartum women
- Healthcare workers: doctors, nurses/midwives, pharmacists, laboratory technologists, community health officers
- Health facility managers
- Community leaders
- Policy makers

The sampling of respondents will be purposive but will cut across various categories of stakeholders in the three levels of the health system in the various states.

8.3 Data collection methods

8.3.1 Qualitative data collection

We plan to conduct focus group discussions (FGDs) and key informant interviews (KIIs) with the identified stakeholders in each state. Interview guides will be developed using CFIR. The implementation climate and outcomes will be explored, as well as barriers and facilitators to successful implementation. The implementation research questions include:

- What are the perspectives of patients, health workers and other key stakeholders regarding the administration of intravenous iron infusion for the treatment of post-partum anemia?
- How feasible is it to implement intravenous iron as a new management strategy for post-partum anemia?
- What factors could prevent or obstruct the adoption and routine administration of intravenous iron infusion for the treatment of post-partum anemia?
- What is the acceptability of the administration of intravenous iron infusion for the treatment of post-partum anemia to health workers, patients, and other key stakeholders in the health system?

While FGDs were chosen because the interaction of members within stakeholder groups will be essential to providing the most robust description of stakeholder's perception of implementation outcomes, KIIs provide an opportunity to have one-on-one in-depth discussions and are more practical to set up for the identified stakeholders.

Table 5 details the target stakeholders and their numbers for each type of stakeholder and across each state.

Table 5: Target stakeholders for qualitative data collection

Target stakeholders	Data collection method	Number per state	Number overall
Postpartum women	FGD	1	4
Healthcare workers	FGD	1	4
Male partners	FGD	1	4
Total FGDs		3	12
Postpartum women with past or current anemia treatment	KII	3	12
Apex healthcare workers	KII	5	20
Health facility managers	KII	1	4
Community leaders	KII	1	4
State policy makers	KII	2	8
Total KIIs		12	48

The final sample size will depend on achieving data saturation (a point in data collection when no additional issues or insights are identified from interviewing additional participants).

8.3.1.1 Conduct of FGDs

A convenience sample of 8 to 12 participants will be invited to participate in each FGD. Verbal consent using a script designed for the study will be sought and received from the participants before commencement. At the beginning of the FGD, socio-demographic data will be collected from participants using a socio-demographic form designed for the study and they will be given identification numbers or nicknames. The sessions will be audio-recorded with consent. One note taker will observe the participants' interaction, body language and the environment in general. The moderator will be a trained research assistant with prior experience facilitating FGDs and with bilingual capacity in English language and any of the local dialects dominantly spoken in the four states (Yoruba, Hausa, or Pidgin English). All interviews will be conducted with the FGD guides purposefully designed for the different categories of stakeholders and encourage active discussion, participation and interaction among the individuals taking part in the FGD. They will be initially written in English and forward translated into the local dialects. During the FGDs, participants will be asked open-ended questions and allowed to provide their perspectives on each issue. Further probing and follow-up questions will be done to provide clarity and lucidity. The sessions will be held in a comfortable, convenient, and accessible place. Each session will last between 60 to 90 minutes.

8.3.1.2 Conduct of KIIs

The KIIs will be conducted by a trained research assistant with prior experience conducting KIIs in a setting that will be convenient for the participants. Most interviews will be face to face except where not feasible, for example with policy makers. In such cases, virtual interviews will be conducted. Verbal consent using a script designed for the study will be sought and received from the participants before commencement. Socio-demographic data will be collected from participants using a socio-demographic form designed for the study. All interviews will be audio recorded. The KIIs will be moderated by the same trained research assistants using KII guides designed for the different stakeholders.

